### ***Minimization of Risks:***

The criteria for subject selection, methods, personnel, facilities, and training that have been specified for this study are intended to minimize the risk to subjects undergoing this procedure. Subjects will be screened carefully prior to enrollment in the study to confirm compliance with the study inclusion and exclusion criteria.

Participating investigators will be experienced and skilled in performing electrophysiology studies, intracardiac mapping, and ablation of AF with the use of the RF ablation catheters. Procedures will be performed in electrophysiology laboratories, with the assistance of skilled nurses and technicians. The laboratory will contain sufficient resuscitative equipment and facilities to manage any potential complication. Cardiac surgical facilities, as well as a qualified cardiovascular surgeon, will be available during the ablation procedure in the event that surgical intervention becomes necessary.

Ablation procedures with the THERMOCOOL® family of catheters will be performed according to the product Instructions for Use, including but not limited to instructions regarding indications and contraindications for using these devices.

***Precautions:***

Invasive electrophysiological evaluation and catheter ablation may impart some degree of risk to the patient. The risk of serious complications is generally related to the severity of cardiac disease. The degree of risk of the electrophysiological and catheter ablation procedures and the potential benefit of the treatment of symptomatic PAF should be determined by a qualified physician. Failure to observe all contraindications, warnings, and precautions, as listed in the Instructions for Use may result in procedural complications. Procedural complications include: cardiovascular injury or perforation with or without cardiac tamponade, pulmonary embolus, tricuspid regurgitation, MI, bleeding at the catheter insertion site, sepsis, and death.

***Potential Benefit:***

The direct benefit for patients undergoing radiofrequency catheter ablation is the potential elimination of AF episodes. It is furthermore expected that quality of life will improve and less frequent hospitalization will be required. The information gathered during the conduct of this study may be of benefit in the future for the treatment of patients with atrial fibrillation.

## Appendix B: Guidelines and Restrictions for the ATTEST Protocol Regarding Cross-over from the Drug (Control) Group

1. Guidelines and principles for cross-over are to be followed by the investigator as laid down in this document and in the protocol.
2. It is the intent of the Sponsor and organizers of this study that cross-over be significantly reduced from published rates quoted in previous drug versus ablation trials.
3. The crossing over from the drug group undermines the tenets of equipoise that are intended in: (a) the study's collective inclusion/exclusion criteria for all subjects; (b) the eligibility of all subjects at study onset to be randomized to either treatment group; and, (c) the intended balance of AF severity, drug history, concurrent illnesses (HATCH score severity), demographics, and other characteristics, such that legitimate statements might be made in comparing the outcomes of medical management versus ablation therapy. The nature and conditions for cross-over from the Control (AAD therapy) Group to the Test (PVI) Group, in a randomized controlled study, are not well understood and are multi-factorial. Thus, any assumptions that subjects crossing over reflect the general demographics, disease severity, and extent of disease progression within either study group at randomization cannot be held with certainty.
4. One could justifiably argue that those most likely to suffer severe side effect reactions from AAD therapy might be those who take their drugs sporadically, take drugs sometimes too close together (shortened inter-dose time interval), suffer rebound effects from resumption of drugs after a drug holiday, and who do not heed the warnings of physicians/pharmacists about mixing drugs for AF/AT with those for other chronic diseases. One might further argue that those with heightened disease progression, as noted in published literature, would be among the oldest in their randomized study group and that their baseline HATCH scores are likely to be high as well, which is consistent with elderly patients. If one or more of these assumptions are true, those most likely to seek cross-over from the drug group would be among the aforementioned, resulting in a relatively younger, healthier, and more compliant group of subjects remaining in the drug group over the whole 3 year study period. In this context, extensive cross-over certainly would erode equipoise.
5. The recognized reasons for patients not doing well on drug therapy are as follows:
  - a. Patients failing to take the medication as prescribed – called “non-adherence”:
    - i. Missed days (drug holidays) – recurring disease symptoms or sudden drug-related side effects, if drug rebound effect, after resuming medication.
    - ii. Irregular timing, resulting in low concentrations of active drug at some points or too high concentrations of active drug when medication is taken at close intervals (may manifest as side effect problem).
    - iii. Medication dropout – patient takes no drug but does not share this information with his/her physician – unexpected disease progression.
  - b. Patient cannot tolerate medication, even if compliant with prescribed regimen (side effects):
    - i. Sensitivity to the prescribed AAD.
    - ii. Concurrent prescribed medications for other chronic diseases are contraindicated for the particular AAD prescribed.
6. When a subject complains to his/her Investigator about the medication and requests a cross-over to receive ablation, the Investigator will have little idea of the root cause of the subject's medication-related problem.

A cross-over management algorithmh could be used to help sort out disease progression issues from drug-related problems.

7. The following guidelines should be addressed by each investigator, prior to making a decision on a subject:

REASON TO INDUCE CROSS-OVER	REASON TO AVOID CROSS-OVER

 
1. Severe symptoms of AF in the absence of evidence that the subject was not taking the prescribed medication and consensus that further medication would be unsuccessful.
 
2. Severe side effects or AF symptoms, evidence of adherence to the prescribed AAD regimen, and no other drug options to which to switch the subject.
 
	
 
1. Evidence that the subject did not take the medications as prescribed and/or took concurrent incompatible medications for other chronic diseases – this subject should undergo Medication Managementi and then return to the hospital 3 weeks later for re-evaluation.
 
2. Evidence not sufficiently strong to merit cross-over, in the minds of the Investigator..
 

h A copy of this algorithm will be available to investigators in this trial as a reference guide to managing subjects with difficulties with their prescribed AAD.

i Medication management includes reviewing all medications taken and an attempt to identify drugs with possible incompatibility with AAD medication(s); review and manage drug taking routine: timing - warning about taking drugs too close together or too far apart; warning about drug holidays and dangers; discuss taking with or without food, as prescribed; coach to use robust routines (taking pills same time each day); pill organizers; and/or recruitment of family to assist subject.

## Appendix C: Justification for AF Disease Progression Rate Estimates

### 1. Introduction

The study of Atrial Fibrillation Progression Trial (ATTEST) is to determine whether early RF ablation intervention using the CARTO® 3 System, CARTO® XP or CARTO® RMT System and THERMOCOOL® Catheter family in the paroxysmal AF (PAF) population delays or prevents progression of AF compared with conventional drug therapy (either rate or rhythm control) using current AF management guidelines. The rates of disease progression at the 3 year follow-up for the ablation group and drug group were estimated at 5% and 25% respectively. This document is to justify these estimates using DerSimonian and Laird meta-analysis method.

### 2. Methodology

The weighted noniterative DerSimonian and Laird random effects model was used to synthesize information from relevant literature studies. In this approach, we assume that there is a distribution of treatment effects and utilize the observed effects from individual studies to estimate this distribution. This approach estimates the magnitude of the heterogeneity, and assigns a greater variability to the estimate of overall treatment effect to account for this heterogeneity. The approach allows for treatment effects to vary across studies and provides an objective and more conservative method for weighting.

### 3. Literature Search

An independent research group (S2 Statistical Solutions) conducted a literature search on AF disease progression outcomes, according to a prospective work plan. Published studies (1990-2011) were searched via PubMed, and unpublished studies were sought from abstracts and presentations at recent professional meetings. Fifty studies meeting inclusion criteria were identified, of which 4 compared catheter ablation to medical treatment. Details of these comparative studies are shown in Tables C1 and C2.

### 4. Meta-Analysis Results

The four comparative studies have different follow-up time. Their disease progression rates at 3 years follow-up are estimated assuming a linear increase of subjects with disease progression over time. The study characteristics and disease progression rates for the ablation arm are summarized in Table C1. The weighted estimate for disease progression of ablation treatment at 3 years follow-up combining the four comparative studies, using non-iterative weighted DerSimonian and Laird random effects model, is 5.6% with the 95% interval of 0.4% - 47.9%.

**Table C1. Literature Studies for Ablation Arm**

Author	Study Design	AF Type at Baseline	Follow-up time (months)	Disease Progression Rate at Study Follow-up Time	Disease Progression Rate at 3 Year Follow-up Time	95% CI
Santinelli 2009 (APAF)	RCT	Paroxysmal to persistent/ permanent	48	1% (1/99)	1% (1/99)	(0.0% – 5.5%)
Dabrowski 2010	Comparative (non-RCT)	Paroxysmal to persistent/ permanent	12	0% (0/6)	0% (0/6)	(0.0% - 45.9%)
De Vos 2010	Comparative (non-RCT)	Paroxysmal to persistent/ permanent	12	6.5% (4/61)	19.7% (12/61)	(10.6% - 31.8%)
Pappone 2008	Comparative (non-RCT)	Paroxysmal to persistent/ permanent	60	0% (0/11)	0% (0/11)	(0.0% - 28.5%)

The four comparative studies have different follow-up time. Their disease progression rates at 3 years follow-up are estimated assuming a linear increase of subjects with disease progression over time. The study characteristics and disease progression rates for the drug arm are summarized in Table C2. The weighted estimate for disease progression of drug therapy at 3 years follow-up combining the four comparative studies, using non-iterative weighted DerSimonian and Laird random effects model, is 26.4% with the 95% interval of 14.8% - 42.6%.

**Table C2. Literature Studies for Drug Therapy**

Author	Study Design	AF Type at Baseline	Follow-up time (months)	Disease Progression at Study Follow-up Time	Disease Progression at 3 Year Follow-up Time	95% CI
Santinelli 2009 (APAF)	RCT	Paroxysmal to persistent/permanent	48	2% (2/99)	1.5% (1.5/99)	(0.0% - 3.9%)
Dabrowski 2010	Comparative (non-RCT)	Paroxysmal to persistent/permanent	12	10% (15/148) Subgroups: Parox to perm: 0% (0/79) Pers to perm: 20% (15/75)	30.4% (45/148)	(23.1% - 38.5%)
De Vos 2010	Comparative (non-RCT)	Paroxysmal to persistent/permanent	12	15% (174/1158)	45.1% (522/1158)	(42.2% - 48.0%)
Pappone 2008	Comparative (non-RCT)	Paroxysmal to persistent/permanent	60	53% (24/45)	25.5% (14/45)	(14.7% - 39.0%)

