## 5.0 Introduction

### 5.1 Background

Atrial fibrillation is the most common cardiac arrhythmia, with prevalence ranging from 0.1% in adults under 55 to 9% in adults over 80 years old. Patients with atrial fibrillation (AF) are at increased risk of stroke, cardiac dysfunction, and death, and may also experience an impaired quality of life due to AF symptoms. Frequency and duration of AF episodes vary, with ACC/AHA/ESC guidelines dividing the condition into paroxysmal, persistent, and permanent types. Transition from one form to another occurs, with episodes generally increasing in frequency and eventually failing to respond to attempts to restore sinus rhythm. Rates of disease progression are not well established, especially in regard to updated classification schemes and in the context of current AF management.

Rates of progression (from paroxysmal AF to more frequent and intractable forms) of up to 30% at 5 years have been reported, with annual risk estimates generally 3-6%. In the first year of observation, rates of progression of 8-15% have been reported for paroxysmal AF. Two studies with follow-up of 8 and 14 years reported well over half of all paroxysmal AF patients eventually progressing to persistent or permanent AF. In contrast, a Mayo Clinic study of lone AF (no hypertension or structural heart disease, diagnosed before age 60) found only 31% of patients progressing over 25 years of follow-up, with mortality rates similar to age- and gender- matched population controls.

Variation in reported rates of AF progression is certainly due in part to the varying definitions used and in the baseline populations studied. The most common definitions in recent published studies are consistent with recommended terminology of paroxysmal, persistent, and permanent AF from ACC/AHA/ESC guidelines. Briefly, paroxysmal AF is defined as recurrent AF that terminates spontaneously within 7 days. Persistent AF is defined as AF sustained beyond 7 days, or lasting less than 7 days but necessitating pharmacologic or electrical cardioversion. Permanent AF is long-standing AF in which cardioversion has failed or is no longer attempted. More recently, the HRS/EHRA/ECAS Consensus Statement includes similar definitions for paroxysmal and persistent AF with long standing persistent

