Variables such as patient age and the presence of comorbidities must also be considered when determining rates of AF progression. Age is the most well-studied and consistently significant factor associated with AF progression. Two studies quantifying the increased risk of AF progression for each decade of age found 40% and 82% increases in risk, respectively. Left atrial (LA) size/volume and hypertension have been frequently studied, with LA volume somewhat more likely to be significant in univariate analyses but not significant in predictive multivariate models. A study from Japan focused on LA wall thickness as a marker of structural remodeling; the authors suggested it to be a stronger predictor of AF progression than LA volume in their cohort of patients. Valvular disease and heart failure were each reported as significant in 4 studies using multivariate models. Valvular disease (univariate or multivariate analyses) and heart failure have also been reported as linked to AF progression. In one study, a composite score (HATCH score), which incorporates hypertension (1 point), age >75 years (1 point), stroke/TIA (2 points), COPD (1 point), and heart failure (2 points), was found to be strongly predictive of AF progression; patients with a moderate to high HATCH score (2-7 points) faced a 25-40% annual risk of AF progression, as compared to below 10% for patients scoring 0 or 1.

In another AF study, the HATCH score was not found to be predictive of AF progression among patients treated by catheter ablation.

The predictive power of patient age seems sensible in the context of AF as a self-perpetuating arrhythmia with interdependent mechanisms. Animal studies of atrial remodeling have proposed that “AF begets AF.” Experimental induction of sustained AF in dogs and in goats support this model. Changes to atrial architecture (fibrotic disorganization and increased atrial size) have also been documented in these animal models. With animal models supporting the concept that “AF begets AF”, similar progression, though not well-studied, is thought to occur in humans, which may warrant treatment (either with AADs or catheter ablation) to delay or prevent such progression and/or changes.

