#### 9.4 Study Exclusion Criteria

1. Patients awaiting cardiac transplantation or other cardiac surgery.
2. Acute illness (ongoing) or active systemic infection or sepsis which in the opinion of the investigator, may adversely affect the safety and/or effectiveness of the participant of the study.
3. Reversible causes of AF, e.g. but not limited to thyroid disorders, acute alcohol intoxication, recent major surgical procedures or trauma,...
4. Recent cardiac events including MI, PCI, or valve or bypass surgery in the preceding 3 months.
5. Heart failure decompensation.
6. Previously diagnosed with persistent/permanent AF/AT
7. Previously required cardioversion  $>$ 48 hours after onset of AF/AT
8. Subject having previous TIA or stroke (cerebrovascular accident) one year prior to patient enrolment and/or no sufficient recovery.
9. Pulmonary embolism or recent atrial embolism/thrombosis.
10. Hypertrophic obstructive cardiomyopathy.
11. Class IV angina or Class IV CHF (including past or planned heart transplantation).
12. Mandated anti-arrhythmic drug therapy for disease conditions other than AF.
13. Heritable arrhythmias or increased risk for torsade de pointes with class I or III Drugs.
14. Prior LA catheter ablation with the intention of treating AF; prior surgical interventions for AF such as the MAZE procedure.
15. Prior AV nodal ablation.
16. Patients presenting contra-indications for the study catheter(s), as indicated in the respective Instructions For Use.
17. Contraindication to warfarin, other anticoagulation therapy, or all anti-platelet medications.
18. Medical conditions limiting expected survival to  $<$  3 years.
19. Concurrent participation in any other clinical study.
20. Prior history of non-adherence to prescribed drug regimens.
21. Women of child bearing potential whom are pregnant, lactating, or planning to become pregnant during the course of the trial

NOTE: Prior ablation of the cavo-tricuspid isthmus is not a reason to exclude, if the patient develops subsequent recurrent atrial fibrillation.

NOTE: For patients randomized to the PVI group (Test Group), a Transesophageal Echocardiography (TEE) should be performed (as per standard of care), within 48 hours pre-procedure, to exclude atrial thrombus or other structural contraindications for an ablation procedure.

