### 13.4 Sample Size and Power Calculation

A total sample size of 322 (161:161) subjects will be required to ensure 85% power to detect the effect size measured by negative log of the hazard ratio equal to 1.154f (treatment group over control group). This calculation assumes a 50% cross-over rate from the AAD group to the ablation group, a 10% drop-out rate in each group over the 3 year follow-up period, and 1.5 years accrual time. This calculation is based upon one-sided superiority testing with alpha equal to 0.025. Using meta-analysis, the rates of disease progression at the end of follow-up are estimated to be 25% and 5% in the AAD and ablation group, respectively (see the point estimate justification document for details, Appendix C). The sample size calculation is based upon the method developed by Rubinstein, Gail and Santner (RGS,1981) and also incorporates group sequential design with multiple interim looks.

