## 5. Conclusion

Our point estimates using the DerSimonian and Laird random effects meta-analysis method for disease progression rates at 3 years follow-up in the ablation arm and drug arm are 5.6% and 26.4% respectively, which are consistent with the physicians' estimates of 5% and 25% for ablation and drug therapy in the new study. Therefore, the published literature and experience in AF disease progression support our estimates of disease progression rate at 3 years follow-up and fully support the study design of a randomized trial testing whether early ablation treatment delays or prevents disease progression from paroxysmal AF to persistent or permanent AF compared with drug therapy.

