6. SAMPLE SIZE DETERMINATION

A total sample size of 322 (161:161) subjects will be required to ensure 85% power to detect the effect size measured by negative log of the hazard ratio equal to 1.1541 (treatment group over control group).

$$-\log_e \left(\frac{\hat{\lambda}_t}{\hat{\lambda}_c} \right) = -\log_e \left(\left(-\frac{\log_e(0.95)}{3} \right) / \left(-\frac{\log_e(0.85)}{3} \right) \right) = 1.1541$$

This calculation assumes a 50% cross-over rate from the AAD group to the ablation group, a 10% drop-out rate in each group over the 3 year follow-up period, and 1.5 years accrual time. This calculation is based upon one-sided superiority testing with alpha equal to 0.025. Using meta-analysis, the rates of disease progression at the end of follow-up are estimated to be 25% and 5% in the AAD and ablation group, respectively (see the point estimate justification document for details, Appendix C of the CTP). The cross-over to ablation is reflected in the use of the proportion 0.85 instead of 0.75 in the formula above. The sample size calculation is based upon the method developed by Rubinstein, Gail and Santner⁴ (RGS, 1981) and also incorporates group sequential design with multiple interim looks.

Adaptive Sample Size Re-estimation

Due to the uncertainties associated with the cross-over rate and the effect size, the sample size will be reestimated at the time of the first interim analysis. Conditional power (CP) will be calculated at that time to determine how promising the interim results are. CP is defined as the conditional probability that the final result will exceed a critical value given the data observed thus far, and the assumption that the trend to be observed in the remainder of the study⁵ will follow the expectation, which was used in the original sample size calculation. If the CP is less than 0.3, then the study is considered not promising, and the sample size will not be increased. If the CP is

greater than 0.9, then the study is deemed fully powered and the sample size will not be increased. If the CP falls in the promising zone (0.3-0.9), the sample size will be re-estimated based upon the observed effect size.

In detail, the following formula will be applied to re-estimate the sample size:

$$M = N \left(\frac{\delta}{\Delta} \right)^2$$

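### The 26.4% pooled drug-arm rate behind the 25% control rate includes a study whose 15 events all arose in persistent-AF patients; without it the pool is about 20% (6.5-48.0%), and at that rate power is roughly 16 to 20 points lower

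*Protocol*

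**What the plan says.** Protocol Appendix C, Table C2, lists four studies for the drug arm, all labelled as progression from paroxysmal to persistent or permanent AF. The 12-month non-randomised study with 148 drug-treated patients is shown as "10% (15/148) Subgroups: Parox to perm: 0% (0/79) Pers to perm: 20% (15/75"). It is scaled linearly to 45/148 (30.4%) at three years. The text between Tables C1 and C2 says that the weighted drug-therapy estimate "is 26.4% with the 95% interval of 14.8% - 42.6" per cent.

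The documents describe the origin of the design rates in two ways. The Appendix C conclusion says the pooled figures agree with the physicians' "estimates of 5% and 25% for ablation and drug therapy in the new study", and that literature and experience fully support the design. Protocol 13.4 and SAP 6 instead say: "Using meta-analysis, the rates of disease progression at the end of follow-up are estimated to be 25% and 5" per cent in the drug and ablation groups.

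The 25% is averaged with 5% for 50% cross-over, which gives the 15% in the effect-size formula, the effect size of 1.154 and the 85% power of 322 subjects. Protocol 9.4 excludes patients "Previously diagnosed with persistent/permanent AF/AT".

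**The concern.** The row's label contradicts its content. The 15 events in the total equal the 15 in the persistent stratum, and the paroxysmal stratum has none. Progression from persistent to permanent AF is neither the trial's population nor its endpoint. The row nevertheless carries a large weight and pulls the pool up towards 25%.

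The strata also sum to 79 + 75 = 154, not 148. The difference equals the 6 ablation patients of the same study in Table C1. That is a plausible reading, but the documents do not state it.

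At stake is the support for the stated 85% power. The planned sample-size re-estimation is not an independent safeguard. SAP 6 computes the conditional power that opens or closes re-estimation on the assumption that the remaining trend "will follow the expectation, which was used in the original sample size calculation". An optimistic design rate therefore also raises the figure that decides whether the sample size is revisited. SAP 10.4 uses the same expected effect for futility.

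**Working it through.** **1. Reproduce the printed pool.** DerSimonian-Laird on the logit scale: y = ln[x/(n−x)], v = 1/x + 1/(n−x), τ² = [Q − (k−1)] / [Σw − Σw²/Σw] with w = 1/v, and random-effects weights 1/(v + τ²). Inputs are the three-year values in Table C2. For the 60-month study, the stated linear rule gives 24 × 36/60 = 14.4.

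| Study | x/n | y | v | Weight |
|---|---|---|---|---|
| 48-month randomised | 1.5/99 | −4.174 | 0.677 | 12.5% |
| 12-month, 148 patients | 45/148 | −0.828 | 0.032 | 29.8% |
| 12-month, 1158 patients | 522/1158 | −0.198 | 0.0035 | 31.8% |
| 60-month, 45 patients | 14.4/45 | −0.754 | 0.102 | 25.9% |

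Q = 35.91 and τ² = 0.431. The pooled logit is −1.026 (SE 0.372), which is **26.4% (14.8-42.6%)**, exactly as printed.

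**2. Drop the row.** Q = 25.96 and τ² = 1.100. The pooled logit is −1.371 (SE 0.659), which is **20.2% (6.5-48.0%)**. Keeping only the row's paroxysmal stratum (0/79 with a 0.5 correction) would give about 12.4%. That stratum counts progression to permanent AF only, so dropping the row is the milder correction.

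**3. A separate print error.** Table C2 gives 25.5% (14/45) with interval 14.7-39.0% for the 60-month study. But 14/45 = 31.1%, with exact interval 18.2-46.6%. The printed rate and interval belong to 14/55. Using 14/45 gives a pool of 26.1% and 14/55 gives 24.4%; only 14.4/45 gives 26.4%. This error did not enter the pool.

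**4. Carry the rate into the design.**
- At 25%: (0.25 + 0.05)/2 = 0.15, and −ln[ln 0.95 / ln 0.85] = 1.153 (printed as 1.154).
- At 20.2%: (0.202 + 0.05)/2 = 0.126, and −ln[ln 0.95 / ln 0.874] = 0.965.

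**5. Power by Rubinstein-Gail-Santner.** 161 per arm, 1.5 years accrual plus 3 years, dropout hazard η = −ln(0.9)/3. Expected events per arm are D = 161 × λ/s × [1 − (e^(−3s) − e^(−4.5s))/(1.5s)], with s = λ + η. Power = Φ(δ/√(1/D_t + 1/D_c) − z).
- At 25%: D_t = 9.4, D_c = 27.7, SE 0.378. Power is 86.2% at z = 1.96 and 84.2% at the final Table 6 bound of 2.0507. Both are close to the stated 85%.
- At 20.2%: D_c = 23.4, SE 0.387. Power is 70.4% and 67.2%.

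**6. Power by simulation.** Group-sequential log-rank, 20,000 trials per cell, Table 6 bounds at eight looks, same accrual and dropout.

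| Convention | 25% | 20.2% | Fall (points) |
|---|---|---|---|
| Cited method, z = 1.96 | 86.2% | 70.4% | 15.8 |
| Cited method, z = 2.0507 | 84.2% | 67.2% | 17.0 |
| Simulation, three-year cap per subject | 83.5% (31 events) | 64.1% (27 events) | 19.4 |
| Simulation, follow-up to study end | 90.6% (37 events) | 74.2% (33 events) | 16.4 |

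**7. Conditional power.** Illustration at 25% of 28 events: drift = δ√28/2, and CP = Φ{[0.5Z + 0.75 × drift − 2.0507]/√0.75}. With Z = 0, CP is 0.61 under 1.154 and 0.44 under 0.965, both in the 0.3-0.9 zone. With Z = −1 it is 0.38 against 0.23, on opposite sides of 0.3.

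**8. Other evidence in the documents.** Protocol 5.1 reports progression "with annual risk estimates generally 3-6" per cent, which compounds to 1 − 0.97³ = 8.7% up to 1 − 0.94³ = 16.9% over three years. It also says that patients with HATCH scores of 2-7 "faced a 25-40% annual risk of AF progression".

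**The case against.** The best defence is that no design input is shown to be wrong. The Appendix C conclusion presents 25% as a clinical judgement, and 25% lies well inside 6.5-48.0%. Other evidence points higher: 8-15% progression in the first year alone (Protocol 5.1), 45.1% at three years in the largest study, and high annual risk at HATCH 2-7 in a trial that enrols HATCH 1-4. All of that stands, and it is why the conclusion is weak support and not refutation.

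Cross-over matters as well. Averaging gives cross-over subjects the ablation rate for the full three years, and Appendix B aims to keep cross-over below published rates. With a 20.2% drug rate and an assumed 40% or 30% cross-over, the cited method gives 79-82% or 87-89% power. So the loss shown is conditional on the plan's own 50%.

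Re-estimation uses observed data, and once triggered it sets the sample size from the observed effect. That softens the consequence. It does not make the trigger independent of the design rate, as the Z = −1 case shows.

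Finally, SAP 5.1 records that the study ended early, so design power enters no remaining test. That limits the consequence to what is reported. The current SAP still states 85% power and attributes the rates to meta-analysis.

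**Conclusion.** The concern holds. On Table C2's own figures, the pooled rate cited for the design includes events from a population that the trial excludes. Removing that row lowers the pool from 26.4% (14.8-42.6%) to 20.2% (6.5-48.0%). The 25% rate remains possible, but Appendix C overstates its support, and the documents disagree on whether it came from physicians or from the meta-analysis.

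If 20.2% were the true rate, power of 322 subjects would be roughly 16 to 20 points below its value at 25%, on any single follow-up convention examined. This assumes 5% on ablation, 50% cross-over by simple averaging, exponential hazards and 10% dropout over three years. The table defect and the re-computed pool are certain from the documents; the power figures are a sensitivity analysis, not an estimate of the trial's actual power.

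**What to change.** 1. In Appendix C, re-run the drug-arm pool without the row and report about 20% (6.5-48.0%), or relabel the row and justify keeping it. Reconcile 79 + 75 = 154 with 148.
2. Correct the 25.5% (14/45) entry.
3. State once, consistently in Appendix C, Protocol 13.4 and SAP 6, whether 25% is a physicians' estimate or a meta-analytic one.
4. In Protocol 13.4 and SAP 6, give the supported rate with its interval, and the power of 322 subjects at 25% and at about 20% on one named follow-up convention; for example, 84% and 64% with a three-year cap per subject.

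The cost is text and one recalculation. Enrolment, endpoint, test and boundaries do not change. The price is that the stated support for the power becomes less favourable.
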